## Use the Product Again

Responses to Use the Product Again VAS will be summarized by study product using descriptive statistics.

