The current study will include a pre-specified period of abstinence prior to each study product administration day (approximately 20 hours in Part A and prior to controlled-use session in Part B, and 6 hours between controlled and uncontrolled-use sessions in Part B) to minimize the impact that residual nicotine concentrations may have on baseline pharmacodynamic, PK and physiological measurements. Consistent with previously published studies, the current study will include an ad libitum product use session, which will allow the subject to use the product as they would in a “real-world” scenario with no limitation on amount of product used, for up to 4 hours. Controlled and uncontrolled product use sessions are also included in order to compare the pharmacodynamic effects and patterns of use under conditions where subjects are instructed on how to use the product (i.e., [maximum 3 ± 2 seconds per puff] at approximately 30 ± 5 -second interpuff intervals) versus how they would use the product in a typical situation.

The current study will use measures of urge to smoke, positive effects, intent to use the product again, and negative effects as proxy measures for the relative reinforcing efficacy of VLN cigarettes, own-brand cigarettes and 4 mg nicotine polacrilex gum. The ability of the VLN cigarettes to satisfy the urge to smoke over the short term will be assessed using the “Urge to Smoke” question in the Tobacco/Nicotine Withdrawal Questionnaire measure and positive effects will be assessed using the “Is the product ‘Pleasant’ right now?” question in the Direct Effects of Product Questionnaire; both will be administered as 100-point VAS. The “Use Product

Again” bipolar VAS has been included at the end of the ad libitum use session in Part A and 90 minutes after product use in Part B to evaluate overall reinforcement effects of the test products. Additional subjective effects will be assessed with “at-the-moment” VAS (Direct Effects of Product Questionnaire, Tobacco/Nicotine Withdrawal Questionnaire) during the Controlled and Uncontrolled Use Sessions to evaluate the magnitude, onset, and offset of product effects and withdrawal symptoms during and after controlled use of the study products.

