10.6.2. Secondary Endpoints

The secondary endpoints of this study are as follows:

- Ad libitum Product Use (Part A)
 - Use the Product Again VAS score
 - Product use behavior (number of units consumed, time spent per unit, number of inhalations per cigarette, duration of gum in mouth)
- Controlled and Uncontrolled Product Use (Part B)
 - Tobacco/Nicotine Withdrawal Questionnaire

- $E_{max_item(\text{controlled})}$: The maximum reduction in VAS score for each item^a between pre-use and post-use (i.e., $VAS_{\text{pre-use}1} - VAS_{\text{post-use}1}$) during the first product use in Part B.
- $E_{max_item(\text{uncontrolled})}$: The maximum reduction in VAS score for each item between pre-use and post-use (i.e., $VAS_{\text{pre-use}2} - VAS_{\text{post-use}2}$) during the second product use in Part B.
- Direct Effects of Product Questionnaire
 - $E_{max_item(\text{controlled})}$: The largest VAS score recorded for the response to each item^b during the first product use in Part B.
 - $E_{max_item(\text{uncontrolled})}$: The largest VAS score recorded for the response to each item during the second product use in Part B.
- Product use behavior (Uncontrolled Use Sessions; number of inhalations, duration of inhalations [per puff], duration of gum in mouth).

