12.4.3. Analysis of Pharmacodynamic Measures

12.4.3.1. Part A

Responses to Use the Product Again VAS will be summarized by study product using descriptive statistics (n, mean, SD, median, Q1, Q3, min, max). A summary table of frequencies may also be provided.

Descriptive statistics (n, mean, SD, median, Q1, Q3, min, max) will be provided for amount of product used by product (number of cigarettes for own-brand and VLN cigarettes, and number of nicotine gum pieces), duration of time used (time spent per cigarette and duration of gum in mouth), and number of inhalations (puffs) per cigarette for own-brand and VLN cigarettes.

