## Statistical Analysis of Subjective Effect Parameters

A linear mixed effects model for analysis of variance/covariance (Proc Mixed) will be performed on  $E_{max\_urge}(\text{controlled})$  and  $E_{max\_plst}(\text{controlled})$ . The model will include  $E_{max}$  as the response variable, sequence, study product, and period as fixed model effects, baseline score as a covariate, and subject nested-within sequence as a random effect. Sequence will be tested using subject nested-within-sequence as the error term. Least square mean (LSM) and 95% confidence interval (CI) for each study product group will be provided. Comparisons will be made for Product A vs. B, A vs. C and B vs. C. The comparison between Product A and Product C will be used as a comparison for internal validity. The LSM difference, p-value and 95% CI of the difference will be provided.

The SAS code for the statistical modeling is:

```
Proc MIXED data=test;
  class subject sequence period product;
  model Emax = sequence period product baseline / ddfm=KR;
  random subject (sequence) / type=UN;
  estimate "Product A vs Product B" product 1 0 -1 /cl alpha=0.05;
  estimate "Product A vs Product C" product 1 0 -1 /cl alpha=0.05;
  estimate "Product B vs Product C" product 0 1 -1 /cl alpha=0.05;
  lsmeans product/cl alpha=0.05;
run;
```

The same model will be used for  $E_{max\_urge}(\text{uncontrolled})$  and  $E_{max\_plst}(\text{uncontrolled})$ , and all  $E_{max}$  of other questions in the Tobacco/Nicotine Withdrawal Questionnaire and Direct Effects of Product Questionnaire for the controlled and uncontrolled product uses in Part B. Baseline (pre-use) score will be included as a covariate for all pharmacodynamics measures for which a pre-use score is collected.

The analysis on  $E_{max\_urge(\text{controlled})}$  and  $E_{max\_plist(\text{controlled})}$  will be based on the pharmacodynamic and the completer populations separately.

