## Pharmacodynamic Data

Tables in this section are based on the pharmacodynamic population unless otherwise stated.

Section 14.2.3.1	Summary of Questionnaires Responses
Table 14.2.3.1.1	Use The Product Again – Descriptive Statistics (Pharmacodynamic Population)
Table 14.2.3.1.2	Tobacco/Nicotine Withdrawal – Descriptive Statistics (Pharmacodynamic Population)
Table 14.2.3.1.3	Direct Effect of Product Questionnaire – Descriptive Statistics (Pharmacodynamic Population)
Section 14.2.3.2	Summary of Subjective Effect Parameters
Table 14.2.3.2.1	Summary of Subjective Effect Parameters for Tobacco/Nicotine Withdrawal (Pharmacodynamic Population)
Table 14.2.3.2.2	Summary of Subjective Effect Parameters for Direct Effect of Product Questionnaire (Pharmacodynamic Population)
Section 14.2.3.3	Statistical Analysis of Subjective Effect Parameters
Table 14.2.3.3.1.1	Statistical Analysis of Subjective Effect Parameters for Tobacco/Nicotine Withdrawal – Product A vs Product B (Pharmacodynamic Population)
Table 14.2.3.3.1.2	Statistical Analysis of Subjective Effect Parameters for Tobacco/Nicotine Withdrawal – Product A vs Product C (Pharmacodynamic Population)
Table 14.2.3.3.1.3	Statistical Analysis of Subjective Effect Parameters for Tobacco/Nicotine Withdrawal – Product B vs Product C (Pharmacodynamic Population)
Table 14.2.3.3.1.4	Statistical Analysis of Subjective Effect Parameters for Tobacco/Nicotine Withdrawal (Completer Population)
Table 14.2.3.3.2.1	Statistical Analysis of Subjective Effect Parameters for Direct Effect of Product Questionnaire – Product A vs Product B (Pharmacodynamic Population)
Table 14.2.3.3.2.2	Statistical Analysis of Subjective Effect Parameters for Direct Effect of Product Questionnaire – Product A vs Product C (Pharmacodynamic Population)
Table 14.2.3.3.2.3	Statistical Analysis of Subjective Effect Parameters for Direct Effect of Product Questionnaire – Product B vs Product C (Pharmacodynamic Population)
Table 14.2.3.3.2.4	Statistical Analysis of Subjective Effect Parameters for Direct Effect of Product Questionnaire (Completer Population)

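### Use the Product Again is the only VAS endpoint with no pre-specified between-product difference or confidence interval, and adding one would be cheap

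*SAP*

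**What the plan says.** **Role.** Protocol 7.2 places the scale at the end of each Part A ad libitum session and 90 minutes after use in Part B, "to evaluate overall reinforcement effects of the test products". Protocol 10.5 describes it as reflecting willingness to use the product again and the overall impression of it.

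**Status.** "Use the Product Again VAS score" is a secondary endpoint for Part A in Protocol 10.6.2 and SAP section 4. The Part B 90-minute score is scheduled after both sessions, but neither endpoint list includes it.

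**Analysis.** The SAP states: "Responses to Use the Product Again VAS will be summarized by study product using descriptive statistics". Protocol 12.4.3.1 (Part A) and 12.4.3.2 (Part B) say the same and specify n, mean, SD, median, quartiles, minimum and maximum. A frequency table is promised for Part A in the synopsis and is optional in 12.4.3.1 and 12.4.3.2. The SAP does not mention it.

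**Output.** SAP Table 14.2.3.1.1, in the Pharmacodynamic Population, is the only summary table for the scale. Its shell has columns for Products A, B and C and rows for N, mean (SD), %CV, quartiles, median, minimum and maximum.

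**The other VAS items.** The mixed model covers the two primary endpoints and the Emax "of other questions in the Tobacco/Nicotine Withdrawal Questionnaire and Direct Effects of Product Questionnaire for the controlled and uncontrolled product uses in Part B". For these, "Comparisons will be made for Product A vs. B, A vs. C and B vs. C", each with an LSM difference, p-value and 95% CI.

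**The concern.** The primary objective is relative: VLN cigarettes against own-brand cigarettes and against gum. Each subject uses all three products so that those comparisons can be made within subject. The scale chosen to capture overall reinforcement is nevertheless the one VAS measure left out of the comparative analysis, while items such as Hunger and Awake are included. It is also the only subjective measure in the 4-hour Part A session, which Protocol 7.2 presents as the closest to everyday use.

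Separate means and SDs do not carry the within-subject correlation, so a reader of the table cannot reconstruct a paired interval. SAP section 6 classes any analysis done after database lock as post hoc and exploratory. If the comparison is wanted later, it will have lost its pre-specified standing.

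**Working it through.** **1. Coverage of the comparative analysis.**
- Tobacco/Nicotine Withdrawal: 5 items in 2 sessions, all modelled.
- Direct Effects of Product: 8 items in 2 sessions, all modelled.
- This gives (5 + 8) × 2 = 26 Emax parameters and 26 × 3 = 78 pairwise contrasts.
- Use the Product Again: collected in Part A, Part B controlled and Part B uncontrolled. No contrasts are planned. The SAP's statistical-analysis tables (14.2.3.3.x) cover only the other two questionnaires.

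**2. The plan's own sample-size figure, used only to see what kind of SD it quotes.** Inputs from Protocol 12.2 for Emax_urge (controlled): difference 15.85, SD 28.44, two-sided alpha 0.05, 54 completers.
- Reading the SD as per-product or within-subject: SE = 28.44 × √(2/54) = 5.47, and 15.85/5.47 = 2.90. Noncentral-t power at 54 is 0.81 to 0.82, and the minimum n for 80% power is 52 or 53. This agrees with 54.
- Reading it as the SD of paired differences: minimum n is 28 and power at 54 is 0.98. This does not lead to 54.

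The quoted SDs therefore behave as per-product or within-subject values. They belong to other endpoints and say nothing directly about this scale.

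**3. Precision if the existing model were fitted.** Assumption: within-subject SD s between 20 and 35 points, because the documents give none for this scale. With 54 completers and three periods, residual df = 162 − 54 − 2 − 2 = 104 and t(0.975, 104) = 1.983. Half-width = 1.983 × s × √(2/54) = 0.382 × s.

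| s | 95% CI half-width |
|---|---|
| 20 | 7.6 |
| 28.44 (borrowed from Urge) | 10.9 |
| 31.82 (borrowed from Pleasant) | 12.1 |
| 35 | 13.4 |

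**4. What the by-product summaries lose.** Assume a per-product SD of 30 and N = 54.
- Means and SDs treated as independent: t × 30 × √(2/54) = 11.4 points.
- Paired, with within-subject correlation ρ: 1.983 × 30 × √(2(1 − ρ)/54) = 9.6, 8.1 and 6.3 points at ρ = 0.3, 0.5 and 0.7.

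The planned table does not report ρ, so the reader cannot tell which of these applies.

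**The case against.** The strongest reply is that this is a deliberate and consistent choice. Protocol and SAP agree on descriptive analysis, and SAP section 12 declares no changes. The endpoint is secondary. Protocol 7.2 names urge, positive effects, negative effects and intent to use again together as proxies for reinforcing efficacy, and the first three already get modelled VLN contrasts, including More, Satisfying and Craving. All of that stands. It makes this an improvement to the plan and not the correction of an error.

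Stronger readings are tempting, but the documents do not support them:
- *The trial will yield no VLN comparison on this scale.* The planned table sets the three products side by side. With near-equal numbers in the three sequences, the difference in completers' means approximates the model's difference. What is missing is a pre-specified, period-adjusted estimate with its precision.
- *Only means and SDs are given.* Quartiles, range and %CV are planned, and possibly a frequency table.
- *The Part B score is neglected.* It is absent from the endpoint lists, but Protocol 12.4.3.2 summarises it. The SAP table shell is laid out by visit, session and time point, and individual responses are listed.
- *Part A has no inference because of this gap.* Part A product use is descriptive under a separate provision, in line with an objective to characterise use.
- *The sponsor's SDs fix the precision at about ±11 to ±12 points.* Those SDs belong to Urge and Pleasant. This scale is bipolar with a labelled midpoint, so only an assumed range is defensible.

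**Conclusion.** The point holds as a cheap improvement. Use the Product Again is a secondary endpoint included to evaluate overall reinforcement, and it is the only VAS endpoint with no planned between-product inference in either document. The two primary endpoints and their analysis are untouched, no planned result is biased, and the subject-level data will exist. What is lost is a pre-specified paired difference and interval.

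The interval would be about ±7.6 to ±13.4 points. That rests on 54 completers and an assumed within-subject SD of 20 to 35 points, neither of which is guaranteed for this scale. Even the upper end is informative on a 100-point scale.

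**What to change.** Pre-specify the SAP section 9 mixed model for Use the Product Again before database lock, with these details:

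- **Model.** Sequence, period and product fixed; subject within sequence random; no baseline term, because the scale has no pre-use score.
- **Three separate fits.** Part A, Part B controlled and Part B uncontrolled. Subjects are re-randomised on Day 4, so Part A must use Part A sequence and period.
- **Part A population.** Subjects randomised in Part A with at least one Part A score. The Pharmacodynamic Population requires Part B controlled-session data and would drop anyone who left before then.
- **Contrasts.** A−B, A−C and B−C LSM differences with 95% CIs, labelled secondary. Do not copy the A vs B line of the SAP's pharmacodynamic code: it is written 1 0 -1, identical to A vs C. The pharmacokinetic code has the correct 1 -1 0.
- **Reporting.** Add a results table, and list the Part B 90-minute score as a secondary endpoint.

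The cost is three model runs on data already collected, a few table shells and a small edit to the endpoint list. It also adds 3 × 3 = 9 unadjusted secondary comparisons to the 78 already planned. The protocol makes no multiplicity adjustment, so no alpha allocation changes.

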## Pharmacokinetic

### Concentration Data

Nicotine plasma concentrations produced by the administration of the study products will be determined to establish the PK profile of each treatment.

Concentrations that are below the limit of quantitation (BLQ) will be treated as zero for descriptive statistics.

Nicotine baseline adjusted concentration will be calculated as follows: post-use concentration – pre-use concentration.

Descriptive statistics will be calculated at each individual time point. Plasma concentration data (both unadjusted and baseline-adjusted) will be summarized by treatment using the following descriptive statistics: number of non-missing values (N), minimum (min), arithmetic mean, median, maximum (max), standard deviation (SD) and coefficient of variation (CV%).

The individual plasma concentration/time profiles will be presented using the actual sampling times whereas the mean plasma concentration/time profiles ( $\pm$ SD) will be presented using the nominal sampling times. Concentration profiles will be presented on both linear and semi-log scales.

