7.1.2.3. Part B (Day 4 to 6)

Upon completion of Part A, subjects will be randomized to one of three product sequence groups in Part B, which will consist of 3 study days (Days 4 to 6), with one product per day. Each study

day will consist of: 1) Controlled Product Use Session (10 puffs from their own-brand cigarette or VLN cigarette [maximum 3 ± 2 seconds per puff] at approximately 30 ± 5 -second interpuff intervals^a, or chew the nicotine polacrilex gum using the “chew and park” method for 10 minutes); and 2) Uncontrolled Product Use Session (use of one unit of a product ad libitum for 10 minutes). The Controlled Product Use Session and Uncontrolled Product Use Session will be separated by approximately 6 hours. During Part B, pharmacodynamic measures, PK samples, and product use behavior (Uncontrolled Product Use Session only) will be collected at various time points each day (See [Table 1](#)).

Safety assessments, including AEs, physical examinations, vital signs (respiratory rate, pulse rate, blood pressure, and oral temperature), electrocardiogram (ECG), clinical laboratory tests (clinical chemistry, hematology, urinalysis, and serology), urine drug screen (UDS), and alcohol test will be collected at designated time points throughout the study.

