## Pharmacokinetic Parameters

PK parameters will be derived from the plasma nicotine baseline-adjusted concentrations versus time profiles using a NCA, with Phoenix WinNonlin 6.3 (Model 200-202, extravascular). The following PK parameters will be calculated for controlled and uncontrolled use:

PK Parameter	Definition
$C_{max(\text{controlled})}$	Maximum measured plasma nicotine concentration during the Controlled Use Session
$C_{max(\text{uncontrolled})}$	Maximum measured plasma nicotine concentration during the Uncontrolled Use Session
$AUC_{(\text{controlled})}$	Area under the nicotine concentration-time curve calculated using linear trapezoidal summation from time zero (defined as the start of controlled use) to 180 minutes (or the last quantifiable concentration during that interval)
$AUC_{(\text{uncontrolled})}$	Area under the nicotine concentration-time curve calculated using linear trapezoidal summation from time 360 (defined as the start of uncontrolled use) to 540 minutes (or the last quantifiable concentration during that interval)
$T_{max(\text{controlled})}$	Time of the maximum measured plasma nicotine concentration during the Controlled Use Session
$T_{max(\text{uncontrolled})}$	Time of the maximum measured plasma nicotine concentration during the Uncontrolled Use Session
$K_{el(\text{controlled})}$	Apparent first-order terminal nicotine elimination rate constant calculated from a semi-log plot of the plasma concentration-time curve of the Controlled Use Session
$K_{el(\text{uncontrolled})}$	Apparent first-order terminal nicotine elimination rate constant calculated from a semi-log plot of the Uncontrolled Use Session

$T_{1/2}(\text{controlled})$	Apparent first-order terminal nicotine elimination half-life calculated as $0.693/K_{\text{el}}$ of the plasma concentration-time curve from time zero (defined as the start of controlled use) to 180 minutes
$T_{1/2}(\text{uncontrolled})$	Apparent first-order terminal nicotine elimination half-life calculated as $0.693/K_{\text{el}}$ of the plasma concentration-time curve from time 360 (defined as the start of uncontrolled use) to 540 minutes

Actual sampling times (relative to the corresponding administration time), will be used for calculation of PK parameters. In the case where less than 3 consecutive measurable concentrations are observed, AUC will not be estimated for that profile.

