The trapezoidal rule (linear trapezoidal linear interpolation) will be used to estimate the area under the curve, and the terminal phase will be estimated by maximizing the coefficient of determination estimated from the log-linear regression model. However,  $t_{1/2}$  and  $K_{\text{el}}$  will not be estimated for individual concentration-time profiles where the terminal log-linear phase cannot be reliably characterized (log linear terminal phase with  $R^2$  of at least 0.8 and using minimum of three data points not including  $C_{\text{max}}$ ).

Plasma nicotine PK parameters will be summarized by treatment using the following descriptive statistics N, min, arithmetic mean, median, max, SD and CV%.

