#### Statistical Analysis of PK Parameters

A linear mixed model for analysis of variance (Proc Mixed) will be performed on the baseline-adjusted log transformed nicotine PK parameters in Part B ( $C_{\text{max}}(\text{controlled})$ ,  $C_{\text{max}}(\text{uncontrolled})$ ,  $AUC_{(\text{controlled})}$  and  $AUC_{(\text{controlled})}$ ). The model will include sequence, study product, and period as fixed effects and subject nested-within sequence as a random effect. Sequence will be tested using subject nested-within sequence as the error term. From each model, the geometric LSM and 95% confidence intervals will be calculated for each study product. Separate analyses will be performed on the parameters calculated for the Controlled and Uncontrolled Use sessions. Geometric mean ratios for each pair comparison, 95% confidence interval and p value will be provided.

The SAS codes for the model will be as follows:

```
Proc MIXED data=test;
  class subject sequence period product;
  model log(Cmax0_180) = sequence period product / ddfm=KR;
  random subject (sequence) / type=UN;
  estimate "Product A vs Product B" product 1 -1 0 /cl alpha=0.05;
  estimate "Product A vs Product C" product 1 0 -1 /cl alpha=0.05;
  estimate "Product B vs Product C" product 0 1 -1 /cl alpha=0.05;
  lsmeans product/cl alpha=0.05;
run;
```

The Hodges-Lehmann's method will be used to estimate the median differences and the 95% confidence interval of  $T_{\text{max}}$  and  $T_{1/2}$  between the products for controlled and uncontrolled use.

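### In the uncontrolled session, subtracting a falling pre-use nicotine level as a constant shortens T1/2 and lowers AUC, and the unadjusted PK parameters promised by the protocol are missing from the SAP

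*SAP*

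**What the plan says.** Protocol section 7.1.2.3 puts two uses of the same product on each Part B day: "The Controlled Product Use Session and Uncontrolled Product Use Session will be separated by approximately 6 hours". Table 1 applies one sampling grid (pre-use, then 2 to 180 min, 15 samples) to both sessions. The 90 PK samples in Appendix 17.1 equal 15 x 2 sessions x 3 days, so each session has its own pre-use sample. Section 7.2 says that the abstinence gaps are there to minimise residual nicotine; it does not claim that none remains.

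SAP section 9 (Concentration Data) sets the adjustment: "Nicotine baseline adjusted concentration will be calculated as follows: post-use concentration – pre-use concentration". It does not say which pre-use sample serves which session. The next step is "PK parameters will be derived from the plasma nicotine baseline-adjusted concentrations versus time profiles using a NCA", and this covers Kel and T1/2. For these, "the terminal phase will be estimated by maximizing the coefficient of determination estimated from the log-linear regression model", with R2 of at least 0.8 and at least three points after Cmax.

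The mixed model is "performed on the baseline-adjusted log transformed nicotine PK parameters in Part B". For Tmax and T1/2, the Hodges-Lehmann "method will be used to estimate the median differences and the 95% confidence interval of" the between-product difference, in both sessions.

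On values below quantitation (BLQ) the SAP says: "Concentrations that are below the limit of quantitation (BLQ) will be treated as zero for descriptive statistics". Their handling in the subtraction and in the non-compartmental analysis (NCA) is not stated, apart from one exclusion: "In the case where less than 3 consecutive measurable concentrations are observed, AUC will not be estimated for that profile".

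The protocol (synopsis and section 12.4.4) promises summaries of derived PK parameters in both forms, unadjusted and baseline-adjusted. In the SAP, Tables 14.2.1.3.1 to 14.2.1.3.6 and Listing 16.2.6.3.3 are all baseline-adjusted. Unadjusted concentrations are kept, but no unadjusted parameters. SAP section 12 declares no departure from the protocol.

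**The concern.** Subtracting a constant is right only if the residue stays level over the next 180 min. Six hours after a use, nicotine is still being eliminated, so by the late samples the true residue is smaller than the value subtracted. Those samples carry the terminal slope and much of the AUC.

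What is at stake is the comparison between products. The error depends on the pre-use level relative to the new increment. The controlled session is fixed at 10 puffs and the uncontrolled one is ad libitum, so this ratio need not be the same for VLN, own-brand and gum. VLN tobacco has 0.4 mg/g, against about 8 to 20 mg for typical cigarettes (Protocol section 5.1), so the VLN pre-use value is the one most likely to be BLQ. If it is then taken as zero, own-brand and gum are over-corrected and VLN is not. The T1/2 comparison would pick up that difference in handling as if it were pharmacokinetic.

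**Working it through.** The documents give no figure to reproduce here, and no half-life, quantitation limit or intake ratio. The values below are assumptions, shown as ranges.

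**Direction (algebra).** Let the residue at the start of the second use be B and the new increment A, both decaying at rate k. The adjusted curve is (A+B)exp(-kt) - B.

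- Its log-slope is k(A+B)exp(-kt) / [(A+B)exp(-kt) - B], which exceeds k whenever B > 0. T1/2 is therefore too short.
- The AUC shortfall is B x [180 - (1 - exp(-180k))/k], which is positive. AUC is therefore too low.
- A constant shift does not move the maximum in time, so Tmax is unaffected.

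**Worked case.** Half-life 120 min, equal uses, instantaneous input, A = 1.

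- k = 0.693/120 = 0.00578 per min, and B = 2^(-360/120) = 0.125.
- Shortfall = 0.125 x (180 - 111.9) = 8.51. The true increment AUC is 111.9, so the loss is 8.51/111.9 = 7.6%.
- The best-R2 rule selects 120, 150 and 180 min. The adjusted values are 1.125 x 0.5 - 0.125 = 0.4375 at 120 min and 1.125 x 0.3536 - 0.125 = 0.2728 at 180 min. The slope is ln(0.4375/0.2728)/60 = 0.00787, so T1/2 = 0.693/0.00787 = 88 min instead of 120.

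**Range.** One compartment, 5-min cigarette input, the protocol's 15 times, linear trapezoid, best-R2 fit after Cmax, equal uses:

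| True half-life (min) | Pre-use / maximum | T1/2 read | Adjusted AUC / true | Adjusted Cmax / true | Unadjusted AUC / true |
|---|---|---|---|---|---|
| 60 | 0.016 | 54.7 | 0.978 | 0.999 | 1.016 |
| 90 | 0.061 | 73.0 | 0.946 | 0.998 | 1.064 |
| 120 | 0.114 | 88.0 | 0.923 | 0.996 | 1.128 |
| 150 | 0.163 | 101.9 | 0.909 | 0.996 | 1.193 |
| 180 | 0.204 | 115.6 | 0.902 | 0.995 | 1.255 |

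R2 is at least 0.999 in every row, so the 0.8 threshold cannot flag the error. The same fit on the unadjusted curve returns 60/90/120/150/180 min.

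**Between products.**

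- *Equal intake ratios, both pre-use values quantifiable, same input.* The errors are equal and cancel. For gum, with an assumed absorption half-life of 10 to 20 min, the AUC ratio to true is 0.974 to 0.876. The cigarette/gum AUC ratio is then off by only 0.978/0.974 = 1.004 to 0.902/0.876 = 1.03.
- *Unequal ratios of first to second intake, 0.67 for one cigarette and 1.5 for the other.* T1/2 reads 56.4/78.4/97.8/116.0/133.8 against 52.0/65.1/74.4/83.1/92.0, a false difference of 4/13/23/33/42 min. The AUC ratio is off by 0.985/0.967 = 1.02 to 0.934/0.853 = 1.10.
- *VLN pre-use BLQ and set to 0, own-brand subtracted, equal uses.* The false VLN minus own-brand T1/2 is 5/17/32/48/64 min (true half-life minus the T1/2 column). If VLN stays quantifiable to 180 min, the VLN/own-brand AUC ratio is multiplied by 1.016/0.978 = 1.04 to 1.255/0.902 = 1.39.

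**Controlled session.** About 18 h after the previous day's second use (24 - 6), the residue is 2^(-1080/60) to 2^(-1080/180), or 0.0004 to 1.6% of the earlier peak. The effect there is likely small.

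**The case against.** Several points on the other side stand.

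- *Baseline adjustment is the protocol's own choice.* Section 12.4.4 specifies a log analysis of adjusted parameters and refers to the SAP for details. Because it asks for both forms, an adjusted Kel and T1/2 is itself implied. A reader might infer that the subtraction formula or the adjusted Kel is an undeclared departure. It is not. The departure is that the unadjusted parameters were dropped.
- *The large T1/2 gaps need a rule that the SAP does not state.* BLQ = 0 is written for descriptive statistics only. If a BLQ pre-use value were treated as missing, there would be no adjusted profile and this false difference would not arise, although low VLN profiles would drop out.
- *The effect on exposure is modest.* Cigarette Cmax is under 1% low, and with equal intake ratios the VLN/own-brand AUC ratio is unbiased by this mechanism.
- *The pre-use sample is not named.* If the morning sample were used for both sessions, the residue would stay in and AUC would be too high. This changes the direction, but it still calls for a sentence in the SAP.

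A stronger reading is that the VLN/own-brand AUC ratio could be badly wrong because of the subtraction. Simulation does not support it. It covered 64 assumption sets: half-life 60 to 180 min, own-brand Cmax about 10 or 20 ng/mL, VLN 2 or 5% of that, quantitation limit 0.2 or 0.5 ng/mL, BLQ = 0. The ratio came out at 0.43 to 1.23 times the truth. Removing the over-correction left it at 0.42 to 1.10, and 32 of the sets run with no residue at all still gave 0.54 to 1.08. The low end is truncation at the last quantifiable value, which Protocol section 10.7 specifies, so that range is not the size of this error.

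**Conclusion.** The point holds for the uncontrolled session. Given the session's own pre-use sample and a quantifiable residue, the direction does not depend on the assumed half-life: T1/2 is too short and AUC too low. The size does depend on it. With one-compartment decay, a half-life of 60 to 180 min and equal cigarette uses, T1/2 reads 55 to 116 min, AUC is 2 to 10% low and Cmax under 1% low. The R2 check does not catch this.

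The planned Hodges-Lehmann T1/2 comparison can therefore show a difference where none exists, if intake ratios differ between products or if one product's pre-use value is BLQ and set to zero. The documents do not show that either will happen; they leave both open.

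The missing unadjusted parameters are a plain mismatch between protocol and SAP and need no assumptions.

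The scope is secondary PK only; the primary VAS endpoints are untouched. A reader might infer that the finding of low VLN exposure is in doubt. That is unlikely to change: if true exposure were 2 to 5% of own-brand (0.4/20 to 0.4/8, tobacco content used as a rough stand-in), the factors 1.04 to 1.39 above would make it read 2.1 to 7.0%.

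**What to change.** 1. Restore unadjusted Cmax, AUC, Kel and T1/2 in the SAP tables and listings, as the protocol promises. Base the between-product T1/2 comparison on the unadjusted profile and keep adjusted Kel and T1/2 as descriptive.
2. Run the same log model on unadjusted Cmax and AUC as support. Note that unadjusted AUC overstates second-use exposure, by about 2 to 26% for cigarettes with equal uses under the assumed half-lives.
3. Name the pre-use sample for each session. State one rule for BLQ pre-use values and one for negative adjusted values in the NCA, the same for all products.
4. Offer a decay-corrected baseline, C(t) - C0 x exp(-Kel x t), as a sensitivity analysis only. It restores AUC in the noise-free model. With BLQ = 0 and truncation, however, it moved the VLN/own-brand AUC ratio further from the truth in 52 of 64 simulated assumption sets, because the two errors partly offset each other.
5. Report by product the number of profiles without AUC or T1/2, and list all these changes in SAP section 12.

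The cost is SAP wording and a little more PK programming and reporting; no new data are needed. None of these steps cures truncation at the last quantifiable value. The counts in step 5 show how many profiles yield no AUC or T1/2.
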